9.2 DOCUMENTATION OF ADVERSE EVENTS

An AE or SAE occurring during the study must be documented in the subject's source documents and on the appropriate eCRF page. Information related to the AE such as onset and cessation date and times, intensity, seriousness, relationship to oral treprostinil (study drug), and outcome is also to be documented in the eCRF (see Appendix 15.4 for definitions). Where possible, AEs should be recorded using standard medical terminology. The Investigator should attempt, if possible, to establish a diagnosis based on the presenting signs and symptoms. If several signs or symptoms are clearly related to a medically-defined diagnosis or syndrome, the diagnosis or syndrome should be recorded on the eCRF page, not the individual signs and symptoms.

9.3 FOLLOW UP OF ADVERSE EVENTS

All AEs should be followed until either resolution (or return to normal or baseline values), until they are judged by the Investigator to no longer be clinically significant, or for at least 30 days if the AE extends beyond the final visit. All SAEs that occur during the study will be followed until resolution, death, or the subject is lost to follow-up even if they are ongoing more than 30 days after completion of the final visit. Supplemental measurements and/or evaluations may be necessary to investigate fully the nature and/or causality of an AE or SAE. This may include additional laboratory tests, diagnostic procedures, or consultation with other healthcare professionals. The eCRF pages should be updated with any new or additional information as appropriate.

If, at any time, the subject withdraws from the study and/or changes from study drug to commercially available Orenitram, any AEs/SAEs that occur on Orenitram (including product use errors, product quality problems, and therapeutic failures) will be reported following local post-marketing reporting requirements or Continued Access Plan local reporting requirements (Section 3.3.2.7). These events will not be included in the protocol analysis.

Pulmonary arterial hypertension symptoms (Section 3.3.1.4) and PAH disease related events (Section 9.1.4) should only be recorded as an AE if the event is serious, new, or unusual with

respect to intensity, frequency, or duration as compared to symptoms in the subject's medical history; or there is a reasonable possibility that the event was caused by the study drug.

9.4 **REPORTING RESPONSIBILITIES OF THE INVESTIGATOR**

All SAEs, regardless of expectedness or causality, must be reported to the sponsor within 24 hours of awareness by fax or email

). A completed SAE Notification Report form along with any relevant hospital records and autopsy reports should be provided to Global Drug Safety at United Therapeutics Corporation. A follow-up SAE Notification Report form must be forwarded to the Global Drug Safety Department at United Therapeutics Corporation within 48 hours of the receipt of any new or updated information. The Investigator must also promptly notify their IRB of the SAE, including any follow-up information, in accordance with applicable national regulations and guidelines set forth by the IRB.

9.5 PREGNANCY

If a study subject becomes pregnant during participation in this clinical study, site staff must notify the sponsor within 24 hours of learning of the pregnancy by completing the Pregnancy Notification Form and submitting via fax or e-mail to Global Drug Safety at United Therapeutics Corporation (**Constitution**). The United Therapeutics Global Drug Safety Department will follow-up with the Investigator to ensure appropriate data are provided regarding the outcome of the pregnancy, and to ask the Investigator to update the Pregnancy Notification Form. Pregnancy only becomes an AE/SAE if there is an abnormal outcome, a spontaneous abortion, an elective termination for medical reasons, or a congenital anomaly in the offspring.

9.6 SAFETY REPORTS

In accordance with national regulations, the Sponsor will notify the appropriate regulatory authority(ies), and all participating Investigators of any AE that is considered to be possibly attributable to oral treprostinil (study drug) and is both serious and unexpected. The Investigator must report these AEs to IRBs in accordance with applicable national regulations and guidelines set forth by the IRB.

10 STATISTICAL CONSIDERATIONS

10.1 DATA PROCESSING

The results of all assessments will be transcribed into an eCRF for each subject who signs an ICF until study completion, or study discontinuation for any reason. A representative from the Sponsor will verify eCRF data fields against source documentation. All data transmitted from the site will be reviewed and entered into a quality assured computerized database. Data clarifications will be generated and the database will be edited as appropriate. The eCRF screens are to be reviewed by the Principal Investigator for completeness and accuracy. The Principal Investigator must electronically sign each subject's eCRF to signify their approval of the data. The Principal Investigator will be required to re-sign an eCRF, if changes are made to a subject's eCRF by the site after the Investigator has applied his/her signature. The database will be final when all outstanding queries have been resolved and all data management quality assurance procedures are complete.

10.2 SAMPLE SIZE

This study is intended to provide descriptive data only. A sample size of 40 subjects (25 transition [IV/SC Remodulin and inhaled] subjects and 15 de novo subjects) was selected for feasibility and to provide a reasonably large experience base with which to draw conclusions about the safety of the proposed protocol for (1) transition from moderate to high doses of IV/SC Remodulin to oral treprostinil, (2) transition from inhaled prostacyclin to oral treprostinil, and (3) initiation of oral treprostinil as add-on therapy in de novo prostacyclin subjects. No formal sample size computation was performed with respect to the primary objective of evaluating safety and tolerability as only descriptive reporting of safety data is planned. The planned sample size of 10-15 subjects within a cohort is appropriate for further characterization of the safety, PK and clinical benefit of oral treprostinil in this symptomatic pediatric subject population with PAH.

10.3 ANALYSIS PLAN

No formal hypotheses will be tested. Descriptive statistics will be used to summarize the endpoints and baseline characteristics. For all summaries, all available data will be presented

TDE-PH-206

with no imputation for any missing data. Subjects will contribute the data available up to the point of study completion, or study discontinuation for any reason. Subjects who receive at least one dose of oral treprostinil will be included in the safety analysis population.

10.3.1 Primary Endpoint(s)

The safety and tolerability of transitioning subjects from IV/SC Remodulin to oral treprostinil (Cohort 1) or from inhaled prostacyclin (Cohort 2) will be based on the percentage of subjects successfully transitioning to oral treprostinil. A successful transition is defined as a subject from Cohort 1 or 2 who is receiving oral treprostinil and no longer receiving IV/SC Remodulin or inhaled prostacyclin, respectively at Week 4 and clinically maintained on oral treprostinil treatment through Week 24. A successful initiation of oral treprostinil (Cohort 3) will be defined as a subject who has been clinically maintained on oral treprostinil through Week 24.

10.3.2 Secondary Endpoint(s)

Analysis of secondary endpoints (6MWD, Borg dyspnea score, functional class, symptoms of PAH, CPET, PedsQL and cMRI parameters) will be descriptive in nature. The PedsQL questionnaire scores will be computed in accordance with the established scoring instructions. Numeric endpoints for post-Baseline assessments will be compared to Baseline using the appropriate statistical test, and p-values will be calculated for descriptive purposes; no formal hypothesis testing is planned.

Plasma samples will be analyzed for treprostinil using a validated bioanalytical plasma assay. Individual and mean treprostinil plasma concentration data and treprostinil pharmacokinetic parameters, such as peak observed plasma concentration (C_{max}), time to peak plasma concentration (T_{max}), area under the plasma concentration-time curve (AUC_{0-inf}), will be determined as able and summarized using descriptive statistics.

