1.2.3 Clinical Pharmacology

The absolute bioavailability following administration of the oral treprostinil extended release tablet is 17% compared with IV Remodulin. Maximum treprostinil concentrations occur between approximately 4 and 6 hours following administration of oral treprostinil in adults.

Following administration, oral treprostinil is widely distributed. Oral treprostinil is approximately 96% protein bound with no effect on warfarin or digoxin displacement. Pharmacokinetic area under the curve (AUC) data; indicate that Day 1 data are predictive of Day 13 and linearity was observed in plasma exposure comparing 1 mg and 2 mg doses in healthy volunteers. Food, particularly a high calorie meal, has been observed to increase absorption and prolong exposure, contributing to the desired pharmacokinetic profile. The relative bioavailability of treprostinil following oral administration of a 1 mg extended release tablet was not significantly altered by meal types ranging from 250 to 500 calories in healthy adult volunteers.

Treprostinil is primarily metabolized by cytochrome (CYP) 2C8 and to a lesser extent by CYP2C9. It is unknown if the metabolism of oral treprostinil will be altered in pediatric patients. A study evaluating the metabolism of paclitaxel by CYP2C8 using pediatric and adult liver microsomes found no age-related differences in metabolism [Blanco, 2000]; however, CYP2C9 activity appears to be increased in children. Clearance is approximately twice that of adult values for several drugs predominately metabolized by CYP2C9, including warfarin, phenytoin, and celecoxib [Anderson, 2009]. Co-administration of oral treprostinil with a strong CYP2C8 inhibitor (*e.g.*, gemfibrozil) has been demonstrated to result in significant elevation of treprostinil plasma concentrations.

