3.3.3 Pharmacokinetics or Other Special Study

3.3.3.1 Pharmacokinetic Sampling

Pharmacokinetic blood sampling will occur twice for each subject in Cohort 1; once during Baseline while the subject is still receiving IV/SC Remodulin prior to starting oral treprostinil, and again at Week 24 when the subject has reached a stable dose of oral treprostinil. Subjects in Cohort 2 and 3 will undergo PK blood sampling at Week 24 only.

All blood samples should be drawn within a ± 10 minute window from their scheduled time point. Record the time and reason for late blood draws and document hemolyzed samples in the eCRF. Hemolyzed blood samples may be redrawn as able. Pharmacokinetic parameters derived from treprostinil plasma concentration-time data will be determined for each subject.

Appendix 15.5 contains a detailed description for the PK blood collection, processing, storage, and shipment of all samples.

Baseline PK Assessment (Cohort 1 Only):

At Baseline subjects in Cohort 1 will undergo an 8-hour PK assessment while receiving IV/SC Remodulin within seven days prior to the first dose of oral treprostinil. Blood samples will be obtained from each subject at time 0 and the following subsequent time points: 4 and 8 hours after time 0 for a total of three blood samples. During the Baseline phase, time 0 should be at the same time of day that it is estimated the Week 24 morning oral treprostinil dose will occur (i.e., if the subject/caregiver anticipates the first daily dose of oral treprostinil at Week 24 will be administered at 8 AM, time 0 should be 8 AM).

Baseline Time Points	Sample Time of Day	Comment (Cohort 1 subjects only while on IV/SC Remodulin)
Time 0	8:00	Estimated time that the morning dose of oral treprostinil will occur at the Week 24 PK assessment.
4 hours	12:00	All subsequent blood draws should occur within a ± 10 minute
8 hours	16:00	window from their scheduled time point. At Baseline all blood draws should be based off of time 0.

Baseline PK Assessment Sample Timelines:

Week 24 PK Assessment (All Cohorts):

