At Week 24 all subjects (all cohorts) will undergo an 8-hour PK assessment while receiving oral treprostinil. No oral treprostinil dose changes are allowed within five days of the Week 24 PK sampling, unless required to protect subject safety. All subjects on a TID dosing regimen will undergo the Week 24 PK assessment based on the first daily dose (morning dose) of oral treprostinil. If a subject is on a QID dosing regimen, the Investigator may conduct the PK assessment based on the first daily dose (morning dose) or the second daily dose (midday dose) at their discretion. The PK assessment dose of oral treprostinil will be taken in the clinic and should occur approximately 8 hours after the prior evening's last oral treprostinil dose for subjects using the morning dose of oral treprostinil should occur approximately 4 to 6 hours after that day's morning dose.

Blood samples will be obtained from each subject at pre-dose (immediately prior [i.e., 10 minutes ±5 minutes] to administration of the PK assessment dose of oral treprostinil) and the following time points: 2, 4, 6, and 8 hours after the PK assessment dose of oral treprostinil (all time points will be based off of the time the PK assessment dose is administered). No other doses of oral treprostinil should be taken during the PK sampling period if the subject is on a TID regimen. The second daily dose of oral treprostinil (midday dose) on a TID regimen will be taken in the clinic and after the final 8-hour PK sample is collected. Subjects on a QID oral treprostinil regimen will take their next daily dose (midday dose or early evening dose [PM #1 dose] based on timing of PK assessment dose) between the 4 and 6 hour time points of the PK sampling (±10 minutes). The PK assessment dose of oral treprostinil must be observed in the clinic by study personnel and taken with food. A

brief description of the food ingested prior to the PK dose of oral treprostinil administration should be recorded in the source and eCRF. Tablets must not be chewed or broken.

Week 24 Time Points	Sample Time of Day	Comment (all cohorts while on oral treprostinil)
Previous evening dose	24:00	The previous evening last dose at the Week 24 PK assessment should be taken approximately 8 hours prior to the next morning oral treprostinil dose.
Pre-dose	7:50	Blood draw should occur 10 minutes ± 5 minutes prior to the morning dose of oral treprostinil.

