8 hours	18:00	oral treprostinil (early evening dose [PM #1]) between the 4 and 6 hour time points of the PK sampling (±10 minutes)

Week 24 QID PK Assessment Based on Midday Dose Sample Timeline:

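### AUC0-inf is the only exposure area the protocol names, but the repeated-dose Week 24 profiles call for AUC0-8 under TID dosing and a separate, labelled summary under QID dosing

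*Protocol*

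**What the plan says.** Describing treprostinil PK in children is a secondary objective (Protocol 2.2).

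- **Parameters.** Protocol 10.3.2 introduces its list with "such as peak observed plasma concentration (C_{max}), time to peak plasma concentration (T_{max}), area under the plasma concentration-time curve (AUC_{0-inf" and says the parameters "will be determined as able and summarized using descriptive statistics". Protocol 10.6 adds a noncompartmental analysis in WinNonlin. No interval AUC appears in either document.
- **Week 24 sampling.** Protocol 3.3.3.1 takes samples pre-dose and at 2, 4, 6 and 8 h. "No oral treprostinil dose changes are allowed within five days of the Week 24 PK sampling", with an exception for safety.
- **TID.** The PK dose comes about 8 h after the last evening dose, and the next dose follows the 8 h sample.
- **QID.** The next dose is taken "between the 4 and 6 hour time points of the PK sampling", and "the Investigator may conduct the PK assessment based on the first daily dose (morning dose) or the second daily dose (midday dose") at their discretion.
- **Peak time.** Protocol 1.2.3: "Maximum treprostinil concentrations occur between approximately 4 and 6 hours following administration of oral treprostinil in adults".
- **SAP.** Section 3 describes TID dosing only. Section 7 admits subjects to the PK population if their samples suffice to estimate the PK parameters, but does not list these. Section 12 names no parameter and leaves the analysis to a separate PK report.

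**The concern.** AUC0-inf describes the whole exposure from a single dose that starts from zero concentration. The Week 24 profiles start from the concentration left by earlier doses. Extrapolating from the 8 h sample to infinity then counts that carry-over as exposure from the dose under study.

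For QID subjects the difficulty is different. Part of a second dose lies inside the 8 h window, so the highest sample, its time and the 8 h area reflect two doses. Neither document separates the regimens. If QID and TID values were summarised together, the table would mix one-dose and two-dose exposure without showing it. This matters because Protocol 1.4 says QID dosing was introduced after interim PK data suggested a better profile in selected children.

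**Working it through.** **1. The plan's own count.** Protocol 15.5 states 8 specimens (24 mL) in Cohort 1 and 5 (15 mL) in Cohorts 2 and 3. Three Baseline plus five Week 24 samples give 8, and 8 x 3 = 24 mL; 5 x 3 = 15 mL. Both reproduce, so each Week 24 profile rests on five samples.

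**2. Is this steady state?** The documents do not use the term. It is inferred from the stable dose and the five-day hold. At the longest half-life assumed below, 5 h, the hold covers 120/5 = 24 half-lives.

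**3. TID principle.** With linear kinetics, equal doses and equal 8 h spacing, the steady-state area over one interval equals the area due to one dose (dose/clearance). The area to infinity is

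AUC0-inf = AUC0-8 + C8/λz,

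so the excess over one dose is C8/λz. Protocol 1.2.3 reports linearity between 1 and 2 mg in healthy volunteers.

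**4. Illustrative model.** From the documents: sampling times, 8 h spacing and peaks at about 4, 5 and 6 h. Assumed, because the documents do not give them: one compartment, 0.5 h lag, constant release over 3.5, 4.5 or 5.5 h, and half-lives of 1 to 5 h. Areas use the linear trapezoid on the five samples and are multiples of one dose's area. λz is set to its true value, which favours AUC0-inf.

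Worked case (half-life 3 h, peak about 5 h): concentrations at 0, 2, 4, 6 and 8 h are 0.0853, 0.1188, 0.1571, 0.1353 and 0.0853.
- AUC0-8 = 2 x (0.0853/2 + 0.1188 + 0.1571 + 0.1353 + 0.0853/2) = 0.993
- λz = 0.693/3 = 0.231 per h, and C8/λz = 0.0853/0.231 = 0.369
- AUC0-inf = 0.993 + 0.369 = 1.362

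All 15 TID scenarios:

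| Assumed half-life | AUC0-inf as a multiple of one dose's area |
|---|---|
| 1 h | 1.01–1.11 |
| 2 h | 1.18–1.26 |
| 3 h | 1.35–1.44 |
| 4 h | 1.52–1.62 |
| 5 h | 1.69–1.80 |

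The extrapolated part is 2% to 44% of AUC0-inf. AUC0-8 from the same samples is 0.98 to 1.06. It is 0.96 to 1.08 when usual spacing is 6/6/12 h and the last gap before the PK dose is 8 h. A second model without lag (release over 4 to 6 h, half-life 1 to 4 h) gives 1.02 to 1.59 for AUC0-inf and 0.93 to 1.00 for the sampled AUC0-8.

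**5. Can AUC0-inf be derived for TID?** One sample follows the observed peak in 5 of the 15 scenarios and two in the other 10. One point gives no slope, and two give a slope with no check on fit.

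**6. QID, morning start.** Same model, with the next dose at 4.5 or 5.5 h, an 8 h overnight gap and 5.33 h spacing on earlier days (30 scenarios). AUC0-8 is 1.12 to 1.60 times one dose's area. The 8 h sample is the highest in 20 of 30 and at or above the 6 h sample in 26 of 30. In those 26 there is no declining phase to extrapolate. Midday-start profiles also span two doses, but their values depend on the assumed morning-to-midday gap, so no range is given.

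**The case against.** The strongest reply is that the plan leaves room. The list in Protocol 10.3.2 is illustrative and qualified, and SAP 12 hands the analysis to a PK report whose own plan may hold the missing rules. That stands. A reader might infer that the protocol requires AUC0-inf or rules out an interval area; the wording supports neither. What remains is that if AUC0-inf is reported it overstates TID exposure, and if it is omitted as not derivable, no other area is named in its place.

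Second, the size rests on assumed kinetics. At a 1 h half-life the excess (1.01 to 1.11) is no larger than the sampling error of AUC0-8 itself. This also stands: the ranges are illustrations, not bounds.

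Third, AUC0-8 matches one dose's exposure only when doses are equal. SAP 11.1 records morning, midday and evening doses separately. In the same model, a morning dose 20% below the other two gives AUC0-8 of 1.01 to 1.12 times that dose's own area (half-lives 1, 3 and 5 h). So AUC0-8 approximates per-dose exposure; it does not equal it in every child.

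Fourth, a reader might want a mandatory QID partial area, cut before the second dose. The documents do not make that clearly better. For a morning start, 0–4 h captures only 0.47 to 0.66 of one dose's area. With the 10-minute tolerance the next dose may come at 3 h 50, which loses the 4 h sample and leaves 0–2 h. It is optional at most.

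Two related gaps might be read as errors but are minor clarifications. Cohort 1 is sampled "once during Baseline while the subject is still receiving IV/SC Remodulin prior to starting oral treprostinil", with no stated summary; AUC0-inf would plausibly just not be computed there. The SAP 12 listing omits the early evening dose that falls inside midday-start QID profiles, but SAP 8 lists all locked data, so the only question is whether the eCRF captures that dose and its time.

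**Conclusion.** The point holds as an unsuitable named parameter together with a missing regimen split. For TID at Week 24, AUC0-8 fits the sampling design, while AUC0-inf is about 1.01 to 1.80 times one dose's area under assumed half-lives of 1 to 5 h, or rests on too few post-peak samples to derive. For QID, the 8 h Cmax, Tmax and AUC span two doses and should not be pooled with TID values.

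The conclusion rests on approximate steady state, linear kinetics and, for the per-dose reading, equal doses. A reader might infer that the PK objective is lost. It is not: individual concentrations are reported, AUC0-8 can be computed from the planned samples, and no test, sample size or primary result depends on this. The change is worth making because it costs little and description is the whole purpose of this objective.

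**What to change.** 1. In Protocol 10.3.2 and the PK analysis instructions, replace AUC0-inf with AUC0-8 (AUC0-tau) for TID profiles at Week 24.
2. In SAP 12 and the PK analysis instructions, summarise TID and QID separately. Flag each QID profile as morning-start or midday-start, label its 8 h Cmax, Tmax and AUC as spanning two doses, and report no AUC0-inf for QID.

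As clarifications only: state the summary for the Cohort 1 infusion Baseline (mean concentration would serve), and confirm that the early evening dose and its time are captured for midday-start QID profiles and named in the SAP 12 listing.

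The cost is wording, slightly more PK analysis and smaller groups once split by regimen. No new blood samples and no change to dosing are needed.

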10.3.3 Safety Analyses

All subjects who receive oral treprostinil (study drug) will be included in the safety population. Statistical summaries of safety data will be descriptive and exploratory in nature,

focusing on the incidence of adverse experiences. The safety data collected in this study will be presented in listings and summary tables.

Treatment-emergent changes in vital signs, ECG recordings, incidence of treatment-emergent AEs, and treatment-emergent changes in clinical laboratory parameters (i.e., hematology, clinical chemistry, and urinalysis) and physical examination will be evaluated.

All AEs will be coded according to the Medical Dictionary for Regulatory Activities (MedDRA) dictionary. The incidence of AEs within each cohort will be presented in summary tables overall and by system organ class and preferred term.

Vital sign and clinical laboratory data collected prior to dosing will serve as Baseline values for evaluation of data collected during the treatment period. Summary statistics will be calculated for measured values at each time point assessed, as well as change from baseline values within each cohort.

No inferential statistical analyses are planned for safety data.

